***Primary Aim:***

1. To compare the efficacy of PENFS therapy versus sham therapy on the improvement of IBS symptom severity in adult IBS patients after 4 weeks of treatment compared to baseline, measured by the mean change in the IBS-SSS.

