***Secondary Aims:***

To compare the efficacy of PENFS therapy versus sham therapy on:

1. the change in mean IBS-SSS at week 8 compared to baseline.
2. the proportion of adult patients with IBS who experience at least a 50-point reduction on the IBS-SSS after 4 weeks of treatment and at the extended follow up period at week 8. These patients are considered clinical responders.
3. the proportion of adult patients with IBS who experience an improvement of  $\geq 30\%$  from baseline in weekly average of the daily worst abdominal pain scores after 4 weeks of treatment. These participants are considered a responder.
4. the change in mean weekly average of the daily worst abdominal pain scores after 4 weeks compared to baseline in adult patients with IBS.
5. the change in average weekly abdominal pain symptoms after 4 weeks of treatment and at extended follow-up (8 weeks) compared to baseline, assessed through the PROMIS Gastrointestinal Belly Pain Scale.
6. the change in average daily stool consistency after 4 weeks of treatment compared to baseline, assessed using the Bristol Stool Form Scale (BSFS).
7. the change in average weekly bowel habits after 4 weeks of treatment and at extended follow-up (8 weeks) compared to baseline, assessed through the PROMIS Gastrointestinal Constipation Scale and Gastrointestinal Diarrhea Scale.
8. the change in average weekly bloating symptoms after 4 weeks of treatment and at extended follow-up (8 weeks) compared to baseline, assessed through the PROMIS Gastrointestinal Gas and Bloating Scale.
9. the change in IBS-QOL in adult patients with IBS after 4 weeks of treatment and at extended follow-up (8 weeks) compared to baseline.
10. the change in resting cardio-autonomic tone, i.e. HRV, over 4 weeks of treatment compared to baseline.
11. the safety and tolerability of PENFS therapy versus sham therapy in adult patients with IBS.

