#### **Primary Endpoint:**

#### **IBS Severity Scoring System (IBS-SSS)**

The primary aim of this study is to compare the efficacy of PENFS versus sham therapy on the improvement of symptom severity after 4 weeks of treatment in adult patients with IBS, using the IBS-SSS. The primary endpoint is the mean change in IBS-SSS at the end of week 4 compared to baseline. This questionnaire is a validated measure of IBS symptom severity and has been shown to be responsive to treatment in different studies. It assesses severity of abdominal pain, frequency of abdominal pain, severity of abdominal distention, dissatisfaction with bowel habits, and interference of IBS with daily life over a 10-day period. Each of the five categories will receive a score from 0-100, and the total IBS-SSS is calculated by taking the sum of these categories (total score range 0-500). Patients will complete the IBS-SSS at week 1, after week 4 of treatment, and at extended follow-up (after 8 weeks). The IBS-SSS will be completed in person at visit 1 and via an online survey at the end of week 4 and during the extended follow-up period at week 8. The online survey will be emailed to the patients the day it is to be completed, and a reminder email will be sent if the survey is not submitted. Improvement in symptom severity will be assessed using a mean change in IBS-SSS score from baseline to 4 weeks after treatment and from baseline to 8 weeks after treatment.

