**Table 1: Timing of PENFS vs Sham Interventions, Questionnaires, and HRV**

	Daily	Baseline	Screening (Visit 1)	End of Week 1 (Visit 2)	End of Week 2 (Visit 3)	End of Week 3 (Visit 4)	End of Week 4	8-week follow up
Consent + Enrollment		X						
History		X						
Daily Worst Abdominal Pain (via Smart Watch)	X	X (daily for 1 week)		X (daily during week 1)	X (daily during week 2)	X (daily during week 3)	X (daily during week 4)	
Daily BSFS		X (daily for 1 week)					X (daily during week 4)	
Physical			X					
PENFS vs Sham Device Placement			X	X	X	X		
Rome IV		X						
Bowel Symptom Questionnaire (BSQ)			X					
UCLA CNSR Participant Demographics			X					
IBS-SSS		X	X	X	X	X	X	X
PROMIS Questionnaires			X	X	X	X	X	X
IBS-QOL			X				X	X
HAD			X					
VSI			X				X	
Heart Rate Variability			X	X	X	X		

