### Statistical Analysis

Fisher tests will be used to evaluate for differences in categorical variables and a 2-tailed t-test and Mann-Whitney-U (MWU) test will be used for assessing differences between normally distributed continuous data and non-normally distributed continuous data, respectively. The data will be analyzed using R statistical analysis software.

The change in IBS-SSS score from baseline will be computed using a generalized linear mixed effect model. We will include treatment, time, and treatment x time as covariates. Tukey's honestly significant difference will be used for multiple comparisons. Data will be analyzed based on a modified intention-to-treat approach. Specifically, patients with less than one full week of data will be excluded from the study.

For all the secondary Aims, a simple 2-sample analysis (T-, MWU or Fisher's) test for changes in outcomes will be performed.

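### Tukey's HSD is attached to the IBS-SSS model with no family named, so the threshold for the single week-4 primary contrast is left open

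*Combined protocol and SAP*

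**What the plan says.** All references are to the combined protocol and SAP.

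- **Primary question.** The Primary Aim compares the arms "after 4 weeks of treatment compared to baseline, measured by the mean change in the IBS-SSS". The Primary Endpoint section agrees: "The primary endpoint is the mean change in IBS-SSS at the end of week 4 compared to baseline". That is two arms, one score and one time.
- **Primary model.** Statistical Analysis (section 9) uses a generalized linear mixed model for IBS-SSS change: "We will include treatment, time, and treatment x time as covariates". The next sentence says that Tukey's "honestly significant difference will be used for multiple comparisons". Neither the family nor the contrast that decides the trial is named.
- **Week 8.** Secondary aim 1 is "the change in mean IBS-SSS at week 8 compared to baseline". The Primary Endpoint section treats both times together: "mean change in IBS-SSS score from baseline to 4 weeks after treatment and from baseline to 8 weeks after treatment". Statistical Analysis then says: "For all the secondary Aims, a simple 2-sample analysis" will be used, with no adjustment stated.
- **IBS-SSS schedule.** The Primary Endpoint section lists three completions: visit 1, the end of week 4, and week 8. Table 1 ("Timing of PENFS vs Sham Interventions, Questionnaires, and HRV") also marks the score at the ends of weeks 1, 2 and 3, and in the baseline column before visit 1.
- **Interim.** Sample Size Calculation plans a comparison of the groups under coded labels, at about one year or at 22 completers per group, whichever is first. It gives no endpoint and no permitted action.

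**The concern.** Tukey's HSD controls error over all pairwise comparisons among a set of means, so it has no defined threshold until the set is named. The primary question involves one pair. Depending on the set chosen, Tukey either changes nothing or charges the primary contrast for comparisons that no aim asks for, such as PENFS at week 4 against sham at week 8.

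Two things are at stake. The first is power: a cell-wise Tukey makes the primary test markedly stricter than a single pre-specified contrast needs to be. The second is pre-specification: with the family unnamed and the IBS-SSS schedule inconsistent, the primary threshold could be settled after the data are in hand.

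**Working it through.** **Inputs from the plan.** Two arms at 1:1 (Randomization and Masking); goal of 35 per arm (Sample Size Calculation); two-tailed testing (Statistical Analysis); post-baseline IBS-SSS at weeks 4 and 8 (Primary Endpoint), or at weeks 1, 2, 3, 4 and 8 (Table 1).

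**Assumptions.** Two-sided alpha 0.05, because none is stated. Equal variances. Degrees of freedom 2 × 35 − 2 = 68. Starting powers of 80% and 95% are hypothetical.

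**The plan's own figure.** The only sample-size figure is 22 per arm for 95% power on a 30% reduction in worst daily pain. It cannot be reproduced, because no rates, SD or alpha are given, and it does not concern IBS-SSS. There is no IBS-SSS power figure to check against.

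**Step 1: number of cells, k.**
- Two arms at week 4 only: k = 2.
- Change at weeks 4 and 8: 2 × 2 = 4.
- Change at the five post-baseline times in Table 1: 2 × 5 = 10.

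**Step 2: threshold.** Tukey critical t = q(0.95; k, 68)/√2, where q is the studentized-range quantile. The nominal level is the two-sided t tail area beyond that value.

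**Step 3: power.** Noncentral t with 68 df. The noncentrality is 2.842 for 80% unadjusted power and 3.657 for 95%. At 35 per arm these are standardized differences of 0.679 and 0.874 (noncentrality divided by √(35/2)).

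| Family | k | Critical t | Nominal level | Power if 80% unadjusted | Power if 95% unadjusted |
|---|---|---|---|---|---|
| Two arms, week 4 | 2 | 1.995 | 0.050 | 80% | 95% |
| Weeks 4 and 8 | 4 | 2.634 | 0.0104 | 58% | 84% |
| Five post-baseline times | 10 | 3.271 | 0.0017 | 34% | 65% |

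With k = 2 the critical value is the ordinary t value, so Tukey corrects nothing. With k = 4, taking 102 or 136 df for the mixed model instead of 68 moves the 58% only to about 59%.

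**Step 4: raw scores instead of change.** If raw IBS-SSS is modelled, the between-arm difference in change is an interaction contrast. It is not a pairwise difference between two cells, so Tukey's HSD does not directly cover it. This is one more way in which the sentence fails to fix the primary test.

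**Step 5: interim, conditional.** Suppose unadjusted success at |z| > 1.96 could be claimed at either look. The correlation between looks is √(22/35) = 0.793, and the bivariate normal gives an overall type I error of 0.0785; simulating t tests gives 0.0789, so about 7.9%. If no efficacy decision is allowed at the interim, there is no inflation.

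**The case against.** The strongest reply is that the plan never says Tukey governs the primary test. It may be meant for supportive comparisons between visits, and then the primary contrast keeps its full level. This stands: the power loss is conditional on an all-cells reading. The text supports neither reading over the other, however, and a single sentence would settle it.

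A reader might go further and infer that the primary endpoint is the only one held to a stricter threshold, while the same score at week 8 is tested unadjusted and could be significant when week 4 is not. The documents do not support that as a finding. If week 8 is in the Tukey family, the same model output gives an adjusted week-8 contrast. The sentence on secondary aims points to a two-sample test, but the model sentence and the Primary Endpoint section treat both times together. Any figure for such disagreement would also need an assumed effect at week 8, four weeks after treatment ends.

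A reader might also infer that the interim inflates type I error. No text provides for an early claim or an early stop. Masking, the goal of 35 per arm and the device request for 35 completers per arm all point to continuing. What remains is that nothing expressly rules out an efficacy decision, and coding the arms does not change a two-sided p-value.

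Finally, an over-strict primary test creates no false claims. True, but it can lose a real effect, for no inferential gain on a single pre-specified contrast.

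**Conclusion.** The point holds in conditional form. One primary contrast needs no adjustment, yet the plan attaches an undefined Tukey adjustment to the model that supplies it. The effect ranges from none (two arms at one time, or supportive comparisons only) to a nominal level of about 0.0104 with 4 cells or 0.0017 with 10. The matching illustrative powers are 58% or 34% from 80%, and 84% or 65% from 95%. They rest on an assumed two-sided 0.05, 35 per arm and hypothetical starting powers. They are not a shortfall against a stated figure: IBS-SSS power is unstated because the plan gives no IBS-SSS difference, SD or alpha. The source of the week-8 result is a real ambiguity in the same section. It is worth fixing because the remedy is almost free. The interim needs only a clarifying sentence.

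**What to change.** In Statistical Analysis:

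1. State that the primary test is the single PENFS-minus-sham difference in week-4 IBS-SSS change from the mixed model, at two-sided 0.05, outside any Tukey adjustment.
2. Keep Tukey, if wanted, only for exploratory comparisons over a named family.
3. State whether the mixed model or the two-sample test gives the week-8 IBS-SSS result.
4. Reconcile the IBS-SSS times in the Primary Endpoint section with Table 1.

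Minor clarification in Sample Size Calculation: state that the coded interim comparison permits no efficacy claim and no early stop for success. The final test then stays at 0.05.

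Cost: a few sentences and no change in sample size. The downsides are that other time points are no longer controlled jointly with week 4 and must be read as secondary or exploratory, and that the interim cannot serve as an informal efficacy readout.

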### ***Assessments and Questionnaires:***

Administration of questionnaires throughout the study is shown in Table 1 and Figure 2.

Patients will provide telephone consent for enrollment into the study. During the this phone call, the investigator will obtain the participant's medical and medication history to check eligibility. After enrollment, patients will complete an online daily questionnaire to assess daily stool consistency (7-point Bristol Stool Form Scale [BSFS]) and a daily question pertaining to daily worst abdominal pain (measured using an 11-point scale) that will be delivered by the smart watch, for one week prior to device placement. If patients do not elect to use the SmartWatch, then they will complete the daily question pertaining to daily worst abdominal pain via an online questionnaire. The questionnaires will provide a baseline for daily worst abdominal pain and stool consistency. In order to be enrolled into the study, patients must have an average daily worst abdominal pain score between 4 and 8, have a minimum of 2 days per week of abdominal pain, and have completed at least 4 out of 7 of the daily worst abdominal pain questionnaires.

If enrollment criteria are met, patients will then present to the UCLA G. Oppenheimer Center for Neurobiology of Stress and Resilience one week after enrollment for their first visit, where they will get a physical examination, complete additional questionnaires, undergo a measurement of HRV, and have the initial PENFS device placed by a trained health care professional (LC, AL, EL). After initial device placement, patients will be instructed to return to UCLA every 7 days (leeway of +/- 2 days in each direction will be allowed) for a total of 4 visits for device replacement and completion of additional questionnaires. Four different devices will be placed in total (at the start of weeks 1, 2, 3, and 4).

Although the IB-Stim device is currently FDA approved for use for 3 consecutive weeks, children in the original study by Kovacic et al actually received 4 consecutive weeks of device treatment. The authors chose to analyze the data after 3 consecutive weeks as children did not return to the clinic after the 4th week of treatment. However, we will analyze IBS symptom severity, abdominal pain, bloating, and bowel habits after the completion of the 4th week of treatment. Again, actual stimulation time is 5 days per week with 2

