#### **Secondary Endpoints:**

#### **IBS-SSS Responder Rate**

In addition, one secondary endpoint of this study will be to assess the proportion of clinical responders, using the IBS-SSS. Clinical responders at the end of 4 weeks and at extended follow-up will be defined as those that have  $\geq 50$ -point decrease on the IBS-SSS score from baseline. This is based upon a study by

Francis et al that demonstrated that a reduction in 50-points correlated with clinically meaningful improvement. Another secondary endpoint is the mean change in IBS-SSS at the end of the extended follow up period at week 8 compared to baseline.

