### **8. Data Collection and Monitoring**

Demographic data and medical history information including co-morbid illness and medication history will be collected and recorded on password protected Excel documents. Questionnaire data collected at different visits will also be stored on password protected Excel documents. We will also monitor for and document any adverse events that occur during this trial. Patients will be given a phone number to call if any questions, concerns, or symptoms related to the device occur.

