## 9. Statistical Considerations

### Sample Size Calculation

Power calculations determined that at least 22 patients would be needed in each arm in order to achieve 95% power to detect at least a 30% reduction in worst daily abdominal pain scores. This power calculation was based on a study by Krasaelap et al, which evaluated the efficacy of PENFS on at least a 30% reduction of worst abdominal pain severity in adolescents with IBS.

We will aim for a sample size that will surpass the number needed to achieve at least 95% power, with a goal of 35 patients in each arm. We will also aim to enroll an additional 5 patients in each arm to account for potential dropouts or losses to follow-up. We will perform an interim analysis about one year after study enrollment has started or when each group has achieved completion of 22 subjects, whichever occurs first (will compare group data but not break the code). An estimate of the study profile is presented in Figure 1.

[figure not shown]

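### The only named analysis set removes patients on an undefined one-week data criterion that most naturally acts after randomisation, and no denominator is named for the safety comparison

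*Combined protocol and SAP*

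**What the plan says.** All references are to the combined protocol and SAP.

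- **Statistical Analysis.** The IBS-SSS change is modelled with a mixed model (treatment, time and their interaction). The same paragraph adopts a modified intention-to-treat approach, defined only by the statement that "patients with less than one full week of data will be excluded from the study". The next paragraph begins "For all the secondary Aims, a simple 2-sample analysis" and goes on to specify t, Mann-Whitney or Fisher tests of change in each outcome. No other population is named.
- **Randomization and Masking.** Patients are randomised once they meet eligibility. Statisticians and physicians do not know the device codes.
- **Assessments and Questionnaires.** For the pre-treatment week, patients must "have completed at least 4 out of 7 of the daily worst abdominal pain questionnaires".
- **Primary Endpoint, IBS-SSS.** The score is taken at visit 1, after week 4 and at week 8. For the two later surveys, "The online survey will be emailed to the patients the day it is to be completed". Table 1 instead marks the IBS-SSS at every visit, including visit 2 at the end of week 1.
- **Secondary Aims, item 11.** The arms are to be compared on "the safety and tolerability of PENFS therapy versus sham therapy in adult patients with IBS".
- **Data Collection and Monitoring.** "We will also monitor for and document any adverse events that occur during this trial". No denominator is given.
- **Sample Size Calculation and the device budget.** The goal is 35 per arm plus 5 for dropout, and a dropout is expected to use 2 devices on average.

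**The concern.** An exclusion based on how much data a patient supplies after randomisation can depend on how that patient fared on the assigned device. Three things follow.

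1. **Usable primary data may be discarded.** A patient who stops in week 1 but returns the week-4 survey has the primary endpoint observed, yet falls outside the only stated set.
2. **The criterion cannot be applied as written.** It names no instrument, no week and no minimum number of entries.
3. **Aim 11 has no stated denominator.** The exclusion is worded as being from the study, not from the efficacy analysis. If it were carried over to safety, patients who gave up the device within days would leave both numerator and denominator, and they are among the most informative about tolerability.

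**Working it through.** **Step 1. When does the rule act?** Randomisation follows eligibility, and the baseline diary already has a 4-of-7 rule. If the one-week criterion meant seven complete baseline days, a patient properly enrolled with four entries would then be excluded, and the two rules would conflict. Acting after randomisation is therefore the natural reading. It is inferred, not stated.

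**Step 2. What is a full week of data?** Table 1 schedules an IBS-SSS at visit 2, which supports reading the rule as reaching that visit. The IBS-SSS section lists no such assessment, so the schedule does not settle it. Visits may also move by 2 days either way, so visit 2 can fall before day 7.

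**Step 3. How many patients? The plan's own figures.**
- Enrolled per arm: 35 + 5 = 40.
- Devices per arm: 35 × 4 + 5 × 2 = 140 + 10 = 150, which matches the budget.

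The 5 dropouts share 10 devices. Assume each had at least one placed. Someone who leaves before visit 2 has used exactly one.
- 2 such leavers: 2 × 1 = 2, leaving 8 devices for 3 patients (3 + 3 + 2). Possible.
- 3 such leavers: 3 × 1 = 3, leaving 7 devices for 2 patients (4 + 3). Possible only if one dropout used all four.
- 4 such leavers: 4 × 1 = 4, leaving 6 devices for 1 patient. Impossible, since the maximum is 4.

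The plan therefore implies about 0 to 2 week-1 leavers per arm, with 3 at the extreme.

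**Step 4. Effect on the primary mean.** Let R be the mean change in retained patients, L the mean in leavers who have a week-4 score, and k their number among 40.

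- All-available mean = [(40 − k)R + kL]/40 = R − k(R − L)/40.
- Shift caused by exclusion = k(R − L)/40.

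The gap R − L is not in the documents. I take 50 points as the central assumption, because the plan states that "a reduction in 50-points correlated with clinically meaningful improvement", and show 25 and 100 as a range.

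| k | gap 25 | gap 50 | gap 100 |
|---|---|---|---|
| 1 | 0.625 | 1.25 | 2.5 |
| 2 | 1.25 | 2.5 | 5.0 |

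At the extreme of k = 3, a 50-point gap gives 3.75. The sign can go either way, and the shift cancels in the treatment difference if both arms are alike. These are simple means, which only approximate the mixed model. If only 36 patients in the arm had a week-4 score (35 completers and one leaver), the figure would be 50/36 = 1.39 instead of 1.25. Leavers with no later IBS-SSS add essentially nothing to a model of change from baseline, so excluding them shifts the estimate by zero.

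**Step 5. Effect on safety if the same set were used.** Assume 3 retained patients in an arm have an adverse event and k more withdraw with one in week 1.
- k = 1: 4/40 = 10.0% among all treated, against 3/39 = 7.7% in the restricted set.
- k = 2: 5/40 = 12.5%, against 3/38 = 7.9%.

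The loss is descriptive. Even 3/40 against 0/40 withdrawals gives a two-sided Fisher p of 0.24.

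**The case against.** The strongest reply is that few patients are involved and the sensible reading does little harm. Much of this stands.

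- **Numbers.** By the plan's own device estimate, week-1 leavers are few. Nothing says that patients who withdraw are still surveyed. If they are not, the bias in the primary estimate is zero.
- **Safety.** A reader might infer that the plan removes week-1 withdrawals from the adverse-event comparison. The documents do not say so. The exclusion sits in the IBS-SSS paragraph, the sentence on secondary aims concerns changes in outcomes (which adverse-event counts are not), and all adverse events are to be documented. What remains is that no denominator is named.
- **Diary reading.** A reader might take the rule to require all seven daily entries, which could remove a large part of the sample. That is implausible beside the 4-of-7 tolerance at baseline and an allowance of only 5 dropouts per arm, and the rule does not mention the diary.
- **Choosing the definition later.** An undefined term can be settled after data are seen. However, statisticians do not know the device codes and the interim look is not to break them, which limits choosing a definition that favours one arm.

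None of this names the instrument, supplies a safety set, or justifies discarding an observed week-4 score. Being a pilot does not change that, since the study is described as evaluating efficacy.

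**Conclusion.** The point holds as a correctable weakness in the choice of analysis set. It does not show that the primary result would be seriously biased. The plan's one named set most naturally excludes after randomisation and can drop patients who have usable IBS-SSS data. The denominator for aim 11 is unnamed.

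The likely effect on the primary estimate is about 1.25 points per excluded leaver with a week-4 score, or 2.5 points for two in one arm only, in either direction. This rests on an assumed 50-point gap, 40 per arm, and leavers who return the week-4 survey. If they do not, it is zero. The safety consequence arises only if the same set is carried over to adverse events, which the text permits but does not state.

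One limit applies: "An estimate of the study profile is presented in Figure 1", and that figure is not available here. These conclusions rest on the available text.

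**What to change.** Before unblinding, amend the Statistical Analysis section as follows.

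1. **Primary efficacy set:** all randomised patients with a baseline IBS-SSS, analysed as assigned, with every available post-baseline IBS-SSS entering the planned mixed model.
2. **Safety and tolerability set:** everyone who had a device placed, named explicitly as the denominator for aim 11.
3. **Sensitivity analysis:** keep the one-week set only here, and define a full week by instrument, time window and minimum data (for example, attendance at visit 2 or the 4-of-7 diary rule already used at baseline).

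It would also help to state whether patients who stop the device still receive the week-4 and week-8 surveys, because the gain from item 1 depends on it.

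The cost is a few sentences and minor extra analysis. The week-4 and week-8 surveys are already planned. The downside is a possibly slightly diluted effect estimate, because patients with little device exposure stay in the comparison.

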### **Heart Rate Variability (HRV)**

HRV will be assessed at baseline/visit 1 and at the end of weeks 1, 2, and 3 (visits 2, 3, and 4 respectively) of treatment, with the goal to determine if HRV (cardio-autonomic tone) changes over 4 weeks of PENFS treatment vs. sham treatment and if HRV predicts response to PENFS. The previous protocols used for HRV analysis have previously been published by members of our research group and are summarized below. HRV will be recorded for 5-minute intervals using a 2-lead electrocardiogram (ECG) attached to patients' upper chest. ECG data will be collected using the BioPac recording system (MP100A-CE; BioPac Inc., Santa Barbara, CA, USA) and will be manually screened for artifacts. The AcqKnowledge peak detection algorithm (V3.8.2; BioPac, Inc.) will be used to determine intervals between adjacent QRS complexes. The interbeat (R-R) interval data will be used for HRV analysis (Kubios HRV 2.0, Biosignal Analysis and Medical Imaging Group, Dept. of Physics, University of Kuopio, Finland). Autoregression (AR) frequency analysis and Fast Fourier transform (FFT) analysis were performed on one continuous 2-minute segment (epoch) of data to avoid inclusion of artifacts, which can distort HRV data. The AR and FFT analyses should yield measures of HF power in normalized power based on a frequency band of 0.15-0.4 Hz and the LF/HF ratio with LF power defined as the interval between 0.04 and 0.15 Hz. A model order of 16 will be used in the AR analysis with no spectral factorization. FFT analysis will use Welch's periodogram method with a window width of 256 s and window overlap of 50%.

The timing of device placements, questionnaires, and HRV assessment is further outlined in Table 1 and Figure 2.

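### HRV (secondary aim 10) is measured at baseline and three later visits, but the plan gives it a simple two-sample test of change with no visit or summary named; one baseline-adjusted repeated-measures analysis would be better defined and more precise

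*Combined protocol and SAP*

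**What the plan says.** Secondary aim 10 is "the change in resting cardio-autonomic tone, i.e. HRV, over 4 weeks of treatment compared to baseline". The Heart Rate Variability section repeats this as a between-arm goal: "with the goal to determine if HRV (cardio-autonomic tone) changes over 4 weeks of PENFS treatment vs. sham treatment". It also sets the recording times: "HRV will be assessed at baseline/visit 1 and at the end of weeks 1, 2, and 3". Table 1 agrees and shows no HRV reading at the end of week 4. The same section describes two spectral methods, autoregressive (AR) and fast Fourier transform (FFT), yielding "measures of HF power in normalized power based on a frequency band of 0.15-0.4 Hz and the LF/HF ratio".

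The Statistical Analysis section gives IBS-SSS a mixed model with treatment, time and their interaction. Tukey's method is mentioned in that paragraph and is not tied to HRV. For the rest the plan says: "For all the secondary Aims, a simple 2-sample analysis", which it specifies as a t, Mann-Whitney or Fisher test of the change in each outcome. No other between-arm analysis of HRV is given.

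**The concern.** A two-sample test needs one number per patient, and for HRV the plan does not say which. PROMIS is also collected weekly, but its section names the contrasts: baseline to week 4 and baseline to week 8. HRV has no such sentence, and the week-4 time point used elsewhere is unavailable because the last HRV reading is at the end of week 3. The analyst would have to choose a visit or a summary, an index and a spectral method with the data in hand.

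The natural default, visit 4 minus visit 1, has two weaknesses. It leaves the week-1 and week-2 readings out of the comparison, although each reading is noisy (one 2-minute epoch). It also subtracts baseline in full rather than adjusting for it, which adds noise when the correlation with baseline is below 1. In addition, the modified intention-to-treat rule excludes only patients with less than one full week of data. A patient who leaves after visit 2 or 3 can therefore be in the analysis set and still contribute nothing to a visit-4 test. At stake are the precision and the pre-specification of the trial's physiological outcome, which is also hypothesis 5.

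**Working it through.** **The plan's own figure.** The documents give no power, variance or effect size for HRV, so there is nothing to reproduce. The 22 per arm in the Sample Size Calculation refers to worst abdominal pain.

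**Inputs from the documents.** One baseline and three post-baseline readings (Heart Rate Variability section and Table 1); 35 completers per arm (Sample Size Calculation); two-tailed testing (Statistical Analysis).

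**Assumptions.** Alpha 0.05; variance 1 at every visit; complete data; correlation either equal between any two readings (rho = 0.4-0.7) or fading as r to the power of weeks apart (r = 0.6-0.8).

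**Formulas** (per-patient variance):
- A. Visit-4 change score: 2(1 - c), where c is the visit 1 to visit 4 correlation (rho, or r^3).
- B. Visit 4 adjusted for baseline: 1 - c^2, so B/A = (1 + c)/2.
- C. Mean of visits 2-4 minus baseline: under equal correlation 4(1 - rho)/3, so C/A = 2/3 for any rho.
- D. Mean of visits 2-4 adjusted for baseline: Var(mean) - Cov(mean, baseline)^2. Under equal correlation this is (1 + 2rho)/3 - rho^2, so D/A = (1 + 3rho)/6.

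**Worked cases for D.**
- rho = 0.4: A = 1.20; D = 0.60 - 0.16 = 0.44.
- rho = 0.7: A = 0.60; D = 0.80 - 0.49 = 0.31.
- r = 0.6: A = 2(1 - 0.216) = 1.568; Var(mean) = [3 + 2(1.2 + 0.36)]/9 = 0.680; Cov = (0.6 + 0.36 + 0.216)/3 = 0.392; D = 0.680 - 0.154 = 0.526.
- r = 0.8: A = 2(1 - 0.512) = 0.976; Var(mean) = [3 + 2(1.6 + 0.64)]/9 = 0.831; Cov = (0.8 + 0.64 + 0.512)/3 = 0.651; D = 0.831 - 0.423 = 0.408.

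| Correlation | B/A | C/A | D/A |
|---|---|---|---|
| equal 0.4 | 0.70 | 0.67 | 0.37 |
| equal 0.7 | 0.85 | 0.67 | 0.52 |
| fading 0.6 | 0.61 | 0.57 | 0.34 |
| fading 0.8 | 0.76 | 0.54 | 0.42 |

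Baseline adjustment alone at visit 4 thus leaves 61-85% of the change-score variance. Averaging alone leaves 54-67%. Both together leave 34-52%.

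**Power if the effect is the same at all three visits.** Take an effect that gives the visit-4 change-score test 80% power, so z = 1.960 + 0.842 = 2.802. Power for D is Phi(2.802/sqrt(D/A) - 1.960). At D/A = 0.52 this is Phi(1.94) = 97%, and at 0.34 it is above 99%. Averaging change scores without adjustment gives 93-97%.

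**Power if the effect builds linearly** (1/3, 2/3, 1 at visits 2, 3, 4). The averaged effect is 2/3 of the final one, so power is Phi((2/3)(2.802)/sqrt(D/A) - 1.960). At D/A = 0.52 this is Phi(0.64) = 74%, and at 0.34 it is Phi(1.26) = 90%, where the visit-4 change-score test has 80%. Against the stricter comparator B, D/B is 0.52-0.61, and the average has 67-73% where a baseline-adjusted visit-4 test has 80%.

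**False positives if each visit were tested at 5%.** Three independent tests give 1 - 0.95^3 = 14.3%. The three changes are correlated, and simulation at 35 per arm gives about 11-13% for one measure.

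**The case against.** Several stronger readings are tempting and the documents do not support them.

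A reader might infer that the plan must either discard two readings or run several tests. It need not: a two-sample test on a mean, an area under the curve or a slope would use all three readings once. The plan defines no such summary, so the gap is that the quantity tested is unspecified.

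A reader might also infer that every visit, or AR and FFT alike, will be tested between arms. Nothing says so. The spectral text is introduced as a summary of published protocols, and visit 4 minus baseline is a fair reading of aim 10 that gives one test per index. The 11-13% is therefore conditional.

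Nor does leaving out two of three readings lose two thirds of the information. The readings are correlated, and averaging the change scores cuts variance by 33% under equal correlation and by 43-46% under fading correlation. The earlier readings also have other stated uses: validating the SmartWatch HRV and asking whether HRV predicts response.

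The strongest point concerns the remedy. An average over weeks 1-3 is a different quantity from the effect at the end of the course, and it loses power if the effect appears late. A supportive visit-4 contrast does not restore that power. This stands as a real cost. Against it, aim 10 asks about change over the course, and the baseline-adjusted average beats the visit-4 change score even under the linear ramp in most of the range examined.

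**Conclusion.** The point holds. Aim 10 has three post-baseline readings and a test that needs one number, with no visit, summary, index or spectral method fixed. If the test is applied to visit 4 alone, it works with roughly two to three times the variance that a baseline-adjusted analysis of all three readings would have (1/0.52 = 1.9 to 1/0.34 = 2.9).

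These figures rest on assumed correlations, equal variances and complete data; the documents give no HRV variance. The power gain also depends on the effect pattern. It is clear for a constant effect. For one building linearly, power is 74-90% against 80%, so a modest loss is possible at high equal correlation. The variance figures do not establish that the plan will inflate its error rate, only that it leaves room for that. The matter is worth correcting but of moderate weight: it is one of eleven secondary aims in a pilot, no power claim attaches to it, and the IBS-SSS endpoint is untouched.

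**What to change.** In the Statistical Analysis section, take aim 10 out of the generic two-sample sentence and state:
- one repeated-measures model of HRV at visits 2, 3 and 4, adjusted for visit-1 HRV, with the treatment effect averaged over the three visits as the single main contrast;
- one index (normalised HF power or LF/HF) and one spectral method (AR or FFT), both named before unblinding;
- the visit-4 contrast, the other index and the other method as supportive only.

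Specify the model itself rather than a test on patient means. The two coincide only with complete data, and the plan allows for 5 dropouts per arm; the model can keep a patient who has only visit 2 or visits 2-3.

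The cost is one or two sentences, with no new data, visits or patients. The scale of the index should be chosen in advance, because the rank-test fallback would no longer apply. The remaining price is the possible loss of power for a late effect. If the investigators expect the effect mainly at the end of treatment, they should say so now and make the baseline-adjusted visit-4 contrast the main one.
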